### 14.2 Data Analysis

Descriptive statistics will be calculated for all measures and variables. We will use 95% CIs for proportions to estimate dichotomous feasibility outcomes (e.g., proportion who agree to participate out of total approached, proportion adherent to SPARC protocol, and proportion who drop out). Frequency distributions will be developed describing participants' reasons for non-adherence and discontinuation of SPARC app use and problems/issues encountered with the app. For continuous usability measures (e.g., frequency, duration of use; surveys-SUS,TSUQ,uMARS), frequency distributions & median and mean responses (with 95% CIs) will be obtained. Mean change and difference in change between the groups from pre-to-post intervention along with their 95% CIs will be reported for all continuous secondary (impact) outcomes (change in PSS-10, FAS, QoL, FSE & TSRQ scores). Preliminary analyses will

SPARC

examine a) underlying distributional properties of all outcome variables b) patterns of missing data, and c) patterns of attrition. Linear mixed-models for repeated measures will be used for the continuous impact measures to obtain estimates of intra-cluster correlation (ICC) & variance estimates along with covariance structure of longitudinal scores used as critical information for sample size calculation of a future efficacy RCT. Based upon Shieh's work, we have inadequate sample size & lack of adequate power to run formal moderator analyses. These analyses will be run in the future appropriately powered RCT to examine impact of socio-demographic variables as potential adherence barriers, as well as potential moderating effects of disease severity (i.e. lung function), fatigue-inducing medications and SPARC meditation adherence on secondary outcomes

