|                                  | International Physical Activity Questionnaire k | X                     | X | X  | X         |

a Age, sex, race, income, education level, employmentb User Version of Mobile App Rating Scale (uMARS;  $\alpha = .90$ , test-retest [2,3 mos] .66, .70)c Patient/Provider SPARC Treatment Satisfaction & Usability Scale (TSUQ;  $\alpha = .82-.96$ , test- retest [1wk] .98)d % adherence to SPARC meditation dose(10min BID for 12 weeks)e Fatigue Self-Efficacy Scale (FSE;  $\alpha = 0.89-0.94$ )f 94 Autonomous Self-Motivation (TSRQ;  $\alpha = .81- .84$ )g 80, Values, Beliefs, Goals Questionnaire (VBG;  $\alpha = .72-.93$ ; Test-retest (2 week) .52-.89)h Fatigue Assessment Scale (FAS;10 items,  $\alpha = 0.8-0.89$ ; Test-retest 0.89)i King's Sarcoidosis Health Questionnaire (KSQ)j Stress (PSS-10 items;  $\alpha = 0.78$ )k International Physical Activity Questionnaire: (test-retest (8-10days) .8)

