## 8 STUDY ENDPOINTS

- The primary measures will be feasibility and usability:  $\geq 80\%$  recruitment,  $\geq 80\%$  retention rates & usability;  $\geq .70$  adherence to twice daily SPARC sessions;  $\geq 75\%$  of sample will score above average on usability & satisfaction questionnaires (SUS  $>68$ , uMARS  $>64$  & TSUQ  $>60$ ).
- Secondary/exploratory efficacy endpoints: Changes in SAF, self-efficacy, stress, autonomous motivation, and QoL.

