**SPARC proof of concept trial:** Based upon our survey responses indicating overall slightly higher preference for the the SPARC prototype app over the Fitbit app in its design, ease of use & self-efficacy of using if free service assistance provided, a 3 mth. proof of concept trial was conducted with SPs with SAF (n=18). The SPARC group engaged in 10 min sessions twice per day and the other group received standard of care (SC). We observed high acceptability (100% participation: 5.5% attrition), self- efficacy for following the SPARC regimen (mean 4.6 on 5-point Likert scale) and adherence over the 3 months (.mo1:81%, mo2:72%, mo3:65%-1 subject began chemotherapy during mth3). As shown in Fig1a&b, the SPARC group reported greater reductions in stress (PSS) and fatigue (FAS) compared to the SC group at months 1 & 3 (all ps <.05- .07). We received helpful suggestions from the participants for further adapting the SPARC app for SPs (e.g., video module having a SP engaging in BAM, several video testimonials by SPs stating how it helps increase energy levels, reduces stress, fatigue and improves quality of sleep; MD give overview of sarcoidosis & role of stress & fatigue).

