### 9.1.3 Randomized Control Trial

**Primary outcomes:** feasibility of enrolling & retaining SPs (benchmarks:  $\geq 80\%$  recruitment,  $\geq 80\%$  retention) and usability (benchmarks:  $\geq 70\%$  adherence to bid SPARC meditation sessions; usability and

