**SPARC App Use:** SPs who randomize into the SPARC group will engage in BAM sessions for 10 min twice daily. The SPARC app is developed based on reviews of the SAF literature, and adaptation of the original TT app using SP & healthcare provider input with low literacy-based strategies and guided by the principles of Self-Determination Theory (SDT). SDT focuses on developing competence (akin to self-efficacy in Social Cognitive Theory) and autonomous regulation. Consistent strong effects of these SDT mediators have been observed for various health behavior changes (e.g., physical activity, smoking cessation, diet). We will promote autonomous motivation by sending tailored motivational/social reinforcement messages linking subjects' behavioral changes (e.g., adherence to BID BAM sessions) to their personal values, beliefs and short/long term goals derived from a branch logic questionnaire (Values, Beliefs, Goals Questionnaire). Domains identified include family, faith, friendships, community activities-membership/volunteer work; attendance and/or participation in leisure, sports & recreational activities and work related events. Domains frequently reported by subjects to be important drivers of behavior were "family, faith and friends." For example, God was often linked to having guided them to a "good doctor" or "pills that work and don't make me as tired." Power of prayer was often noted in conjunction with "praising God and showing thanks for the continued gift of life by treating my body as his temple." Family and community cohesiveness and support, especially activities with friends and family members were primary adherence motivators related to short-term life goals (e.g., increased time gardening, fishing, playing with grandchildren, attending church functions, etc.). Responses will guide delivery of >900 different automated motivational/social encouragement messages based upon levels of adherence to their SPARC regimen. A sample SMS feedback for an adherence score of 1.00 is: "*Way to go! Every day of Taming your tension keeps you on track for (patient identified values, e.g., "many more years watching those grandkids grow up").* If partially or completely non-adherent, he/she might receive: "*You must have been really busy yesterday. Get back on track with Tamer to keep reducing stress & fatigue and plan some special time with your grandkids.*"

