**Table 2. Measurement/Instruments and Time Points for Feasibility Trial**

| Outcomes                                    | Psychometrics  | Time               |
|---|--|--------------------|
| Primary Outcomes                     |  |                    |
| Feasibility and System Usability            | % recruitment, drop-out rate; System Usability Scale(SUS);  User Version of Mobile App Rating Scale (uMARS; $\alpha=.90$ , test-retest [2,3 mos] .66, .70);  Patient/Provider SPARC Treatment Satisfaction & Usability Scale (TSUQ; $\alpha=.82-.96$ , test- retest [1wk] .98);  % adherence to BAM dose(10min BID for 12 weeks) | Week 12            |
| Secondary & Exploratory Outcomes |  |                    |
| SDT Constructs:                             | Competence/self efficacy: Fatigue Self-Efficacy Scale (FSE; $\alpha=0.89-0.94$ );  Autonomous Self-Motivation (TSRQ; $\alpha=.81-.84$ );  Values, Beliefs, Goals Questionnaire (VBG; $\alpha=.72-.93$ ; Test-retest (2 week) .52-.89)  | Week 0 & 12        |
| Fatigue, QoL, Stress, Physical activity     | Fatigue Assessment Scale (FAS;10 items, $\alpha = 0.8-0.89$ ; Test-retest 0.89)  ; QoL scale in King's Sarcoidosis Health Questionnaire (KSQ)  ; Stress (PSS-10 items; $\alpha = 0.78$ )  ,International Physical Activity Questionnaire: test-retest (8-10days) .8)   | Week 0, 4, 12 & 24 |
| Demographic Variables                       | Age, sex, race, income, education level, employment  | Week 0             |

**Data Management:** The Research Electronic Data Capture (REDCap) system will be used for data collection and as the primary database, including assignment of variable names and coding, design of data entry forms, automated data entry error checks, quality control checks, and database access and locking. All assessments and clinical data will be entered into a standardized password-protected database behind MUSC's firewall. Data will be reviewed on a twice-monthly basis. Outlying, inconsistent data values, as well as missing data, will be targets of the data quality review.

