### 14.3 Interpretation of Results

This proposal explores the usability/feasibility of the SPARC App to assess and manage stress. The primary outcomes for this study will be usability/feasibility of the SPARC App. Based upon our proof of concept trial(n=18), we anticipate acceptable participation rates( $\geq 80\%$ ), low drop-out rates( $\leq 20\%$ ), adherence rates ( $\geq .70$  to twice daily 10 min BAM sessions), and usability scores ( $\geq 75\%$  of sample will score above average on SUS, uMARS, TSUQ). We anticipate signals of improvement in the SPARC group in secondary outcomes compared to SC group including changes in fatigue (FAS), stress (PSS), self-efficacy (FSE), autonomous motivation (TSRQ) and QOL.

## 16

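### The adherence benchmark of .70 has no defined summary, and Section 14.2 names only a proportion adherent with no cut-off or target share, so the pass/fail reading of a primary outcome is undetermined

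*Combined protocol and SAP*

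**What the plan says.** **Benchmark.** Section 8 asks for at least .70 "adherence to twice daily SPARC sessions". Section 9.1.3 asks for at least 70% "adherence to bid SPARC meditation sessions". Section 14.3 expects adherence rates of at least .70 "to twice daily 10 min BAM sessions". The synopsis and Section 7 carry the same figure.

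**Measure.** Footnote d of Table 1 gives percent "adherence to SPARC meditation dose(10min BID for 12 weeks", and Table 2 gives percent "adherence to BAM dose(10min BID for 12 weeks", reported at week 12. The app paragraph in Section 9.1.3 treats adherence as graded: "A sample SMS feedback for an adherence score of 1.00 is" introduces one message, and a different one goes to people who are partly or wholly non-adherent.

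**Pilot.** Section 9.1.1 reports adherence of 81% and 72% in months 1 and 2, then "mo3:65%-1 subject began chemotherapy during mth3". Section 14.3 cites this 18-person trial as the basis for its expectations.

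**Analysis.** Section 14.2 gives 95% CIs for proportions to the dichotomous feasibility outcomes, and one of its examples is "proportion adherent to SPARC protocol". Neither a cut-off nor a target share appears anywhere. Section 14.2 also promises descriptive statistics for every measure, and means with 95% CIs for continuous usability measures such as frequency and duration of use.

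**Precision.** Section 14.1 quotes ±0.08 to ±0.13 for categorical feasibility measures, with 50 participants, 25 per group.

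**The concern.** The benchmark and the named analysis describe different quantities. A fraction of prescribed sessions is continuous for each participant and needs a rule for summarising it over participants. A proportion adherent needs a per-participant cut-off and a target share. The plan supplies one number, .70, and does not say which of these it is.

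Where the protocol means a share of participants it says so: the questionnaire benchmark is set at 75% or more of the sample. The adherence benchmark has no such wording, which favours the session-fraction reading.

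Adherence is a primary outcome. If the summary and the cut-off are chosen after the data are seen, that choice can decide whether the benchmark is met.

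**Working it through.** **1. Reproduce the plan's precision.** Wald half-width = 1.96 × √(p(1−p)/n).

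| n | p = .10 or .90 | p = .30 or .70 |
|---|---|---|
| 50 | .083 | .127 |
| 25 | .118 | .180 |

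The quoted ±0.08 to ±0.13 is the n=50 row. App adherence exists only in the SPARC arm, so a proportion adherent has the n=25 row: about ±.18 near .70.

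**2. The prescribed dose.** 2 sessions × 84 days = 168 sessions; .70 × 168 = 117.6 sessions.

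**3. Can the two summaries disagree?** Take 25 SPARC participants and a per-participant cut-off of .70.

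- 14 people at .95 and 11 at .45: mean = (13.30 + 4.95)/25 = .73; share at or above .70 = 14/25 = 56%.
- 18 people at .75 and 7 at .30: mean = (13.50 + 2.10)/25 = .624; share at or above .70 = 18/25 = 72%.

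In the first case the mean meets .70 and the share does not. In the second the reverse holds. Both comparisons apply .70 to the share as well as to the mean.

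**4. Is this a rare accident?** The documents give no between-person SD and no adherence cut-off, so this step is illustrative. Assume a true mean of .727, the simple pilot average (81 + 72 + 65)/3 = 72.7%; Beta-distributed individual adherence; and an SD of .15 to .30. In 100,000 simulated trials of 25 per setting, the mean passes if it is at least .70, and the share passes if at least 70% of participants reach the cut-off.

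| Assumed cut-off | Expected share adherent | Trials where the two verdicts differ |
|---|---|---|
| .50 | .76–.92 | 15–22% |
| .70 | .61–.64 | 41–63% |
| .80 | .36–.56 | 61–81% |

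At cut-offs of .70 and .80 almost all disagreements are a passing mean with a failing share. At .50 most go the other way. The second example in step 3 is therefore possible but uncommon under this Beta model at a .70 cut-off.

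**5. Precision of a mean at n=25.** Half-width = t(24) × SD/√25 = 2.064 × SD/5. For SD .20 this is .083, and for SD .35 it is .144. Both SDs are assumptions.

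**The case against.** Four points on the other side deserve weight.

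- **The mean is inferred.** No section uses that word for adherence. The .70 could be a per-participant cut-off, with the proportion adherent being the share who reach it. Section 14.2 would then fit the benchmark's cut-off, and only the target share would be missing. This reading is possible, but the verdict is still undetermined under it. The pilot does not settle the matter, since Section 9.1.1 does not say whether its percentages are session fractions or shares of people.
- **Section 14.2 leaves room for a mean.** A reader might infer that the plan cannot assess the benchmark. That goes too far: descriptive statistics cover every measure, and mean frequency of use over a fixed prescription is close to session adherence rescaled. What remains is that nothing ties such a mean to .70.
- **No target of 70% of participants exists.** A reader might take the reversals as showing that the plan contradicts itself. The documents do not support that. The reversals show only what happens if .70 is carried over to the share, which the wording leaves open.
- **A mean will not guarantee a clear answer.** At an observed .727 the margin over .70 is .027, while the half-width even at SD .15 is 2.064 × .15/5 = .062. The interval would include .70. This stands, but it reflects the sample size. A defined estimate with an honest interval is what a feasibility study can deliver.

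The study's stated focus on feasibility rather than hypothesis testing lowers the stakes. It does not remove the need to say which estimate a numeric benchmark is compared with.

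**Conclusion.** The point holds as a gap in definition. The benchmark reads most naturally as a fraction of prescribed sessions, its summary over participants is not stated, and the one analysis that names adherence is a dichotomy with neither cut-off nor target. That analysis does not estimate the benchmarked quantity on the natural reading.

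The possibility of reversal is plain arithmetic at n=25. The 41–63% disagreement rate is conditional on the assumed Beta shape, SDs, pilot-based mean and .70 cut-off, and should not be quoted as a forecast. The finding that the Section 14.1 precision corresponds to n=50, and so does not apply to adherence, needs no assumption beyond the Wald formula.

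This should be corrected before analysis. It does not undermine the design or the data collection.

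**What to change.** In Section 14.2, name the adherence estimate that is compared with .70. Suggested content:

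- For each participant randomised to SPARC, adherence is completed sessions divided by 168 prescribed (2 × 84 days). The primary estimate is the mean over all those participants, with a 95% CI based on the SPARC arm (n=25).
- State how sessions after drop-out count. Counting them as not done is the conservative choice. It overlaps somewhat with the retention benchmark and makes the figure slightly less favourable.
- State what heart-rate record counts as a completed session, since Section 9.1.3 monitors compliance that way.
- If the proportion adherent is kept, report it as supportive, with a stated per-participant cut-off (for example .70). Quote its precision at n=25 in Section 14.1, not n=50.

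If the sponsor did intend .70 as a per-participant cut-off, the same section should say so and give the target share. Results by 4-week block are optional; they would show whether adherence declines as it did in the pilot.

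The cost is a few sentences. No new data are needed, because session use is already monitored through the app.

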## 7 STUDY OBJECTIVE

The objective of this proposal is to conduct a randomized control trial evaluating the Sarcoidosis Patient Assessment and Resource Companion (SPARC) App, including assessing the feasibility of our study methodology, and estimating variability of outcomes and treatment effect on stress and fatigue and QOL measures. We hypothesize the SPARC App will be deemed a feasible, acceptable tool with high usability among sarcoidosis patients. Additionally, we expect to experience preliminary signals of clinical efficacy and obtain estimates of variability of changes in secondary outcomes such as perceived stress, fatigue, quality of life and self-efficacy due to engagement in the SPARCs breathing awareness meditation module.

Specific aims of this proposal are:

Specific Aim 1. Conduct a 12 week feasibility RCT with a follow-up at 24 weeks with 50 SPs with SAF. They will be randomly assigned to SPARC or an enhanced attention control group stratified by healthcare provider. They will be evaluated at baseline, 4, 12 and 24 weeks.

2a. Demonstrate feasibility of SPARC (benchmarks:  $\geq 80\%$  recruitment,  $\geq 80\%$  retention rates) and usability ( $\geq .70$  adherence to twice daily SPARC sessions); usability and treatment satisfaction scores:  $\geq 75\%$  will score above average on usability & satisfaction questionnaires (SUS  $>68$ , uMARS  $>64$  & TSUQ  $>60$ ). Back-end analytics will assess uptake of SPARC App (total engagement time) and its features (e.g., frequency of provider service line use, FAQ, video clips- sarcoidosis, fatigue & stress educational modules, sarcoidosis patient testimonials, etc.).

2b. Obtain estimates of variability of changes in secondary outcomes: stress (PSS), SAF,

QoL, fatigue self-efficacy (FSE) & autonomous motivation (TSRQ).

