### 14.1 Sample Size Determination

Focus of this project lies on demonstration of feasibility (recruitment, retention and adherence rates) and usability (frequency, duration of app use; satisfaction/usability surveys-SUS, TSUQ, uMARS) rather than hypothesis-testing. Thus, sample size was determined for pragmatic reasons such as assessment of recruitment, drop-out and adherence rates. For categorical feasibility measures, with 50 SPs (25 per group), we will be able to estimate proportions with precision  $\pm 0.08$  to  $\pm 0.13$  for true population proportion (p) values for each outcome ranging from 0.10 to 0.30 (or correspondingly, from 0.70 to 0.90). For continuous usability measures, 95% confidence intervals (CIs) can be estimated with precisions ranging from  $\pm 0.20$  to  $\pm 0.78$  corresponding to estimated standard deviations (SDs) ranging from 0.5 to 2.0, respectively. For continuous impact measures (PSS,FAS, & QoL, FSE & TSRQ change scores), in intent-to-treat analyses, 95% CI estimates of within-group change scores (pre- to post-treatment) will have precisions ranging from  $\pm 0.1.5$  to  $\pm 2.4$  corresponding to estimated SD of change scores ranging from 3.7 to 6.1, respectively; between-group change scores differences will have precision estimates from  $\pm 2.8$  to  $\pm 3.7$  for SDs of differences in scores from 5.0 to 6.7 SD units.

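### Section 14.2 compares the arms on the secondary outcomes by unadjusted change scores; adjusting for the baseline score already collected would cost almost nothing and give a modest gain in precision.

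*Combined protocol and SAP*

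**What the plan says.** Section 14.2 states the analysis of the continuous secondary outcomes (PSS-10, FAS, QoL, FSE, TSRQ) as follows: "Mean change and difference in change between the groups from pre-to-post intervention along with their 95% CIs will be reported". Section 9.1.3 defines the secondary outcomes in the same way, as group differences in change.

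Section 14.1 bases its precision on that comparison: "between-group change scores differences will have precision estimates from" ±2.8 to ±3.7, "for SDs of differences in scores from 5.0 to 6.7 SD units". For within-group change it uses a different range, "estimated SD of change scores ranging from 3.7 to 6.1".

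Section 14.2 also plans a model: "Linear mixed-models for repeated measures will be used for the continuous impact measures to obtain estimates of intra-cluster correlation (ICC", together with variances and the covariance structure, as input for sizing a later efficacy trial. It lists no fixed effects, baseline term or arm contrast.

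On incomplete data, section 14.1 has the phrase "in intent-to-treat analyses, 95% CI estimates of within-group change scores", and section 14.2 will examine "patterns of missing data". Neither says how a subject without a week-12 score enters the arm difference.

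Table 2 shows that all five scores are collected at week 0. FAS, KSQ and PSS are repeated at weeks 4, 12 and 24; FSE and TSRQ only at week 12.

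**The concern.** Section 7 sets the objective of "estimating variability of outcomes and treatment effect on stress and fatigue and QOL measures". With 25 subjects per arm the intervals for that effect will be wide, so a gain in precision that needs no extra subjects or visits is worth taking. A change score subtracts the whole baseline value, which amounts to fixing the regression slope at 1. Adjustment for baseline estimates the slope and is usually more precise in a randomised trial unless the baseline to follow-up correlation is very high.

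Writing the adjustment down also settles which estimate is the main one before the data are seen. As it stands, an analyst could take the arm difference either from raw change scores or from the mixed model with terms chosen later.

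**Working it through.** **Inputs.** 25 per arm and a change-score SD of 5.0 to 6.7 (section 14.1); drop-out of up to 20% (section 14.3); FAS test-retest 0.89 (Table 2). The baseline to week-12 correlation ρ is not given. I assume 0.3, 0.5, 0.7 and 0.89, with the test-retest figure as an upper anchor.

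**The plan's own figure.** Half-width = 1.96 × SD × √(2/25).
- SD 5.0: 1.96 × 5.0 × 0.2828 = 2.77 (stated 2.8)
- SD 6.7: 1.96 × 6.7 × 0.2828 = 3.71 (stated 3.7)

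The stated range is therefore unadjusted, at full N and without drop-out. With the within-group SDs of 3.7 and 6.1 the same formula gives 2.05 and 3.38; the percentages below do not change.

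**Effect of adjustment, equal variances.** Per subject, Var(change) = 2σ²(1−ρ) and Var(adjusted) = σ²(1−ρ²), so the variance ratio is (1+ρ)/2. The cost of one covariate at N = 50 is √(47/46) × t(47)/t(48) = 1.0114. Width ratio = √((1+ρ)/2) × 1.0114.

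| ρ | Width ratio | Narrower by | Half-width (from ±2.77 to ±3.71) |
|---|---|---|---|
| 0.3 | 0.815 | 18% | ±2.26 to ±3.03 |
| 0.5 | 0.876 | 12% | ±2.43 to ±3.25 |
| 0.7 | 0.932 | 7% | ±2.58 to ±3.46 |
| 0.89 | 0.983 | 2% | ±2.73 to ±3.65 |

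A simulation of 4,000 trials with 25 per arm gave 0.815, 0.874, 0.930 and 0.982. The ratio reaches 1 at ρ of about 0.96. At ρ = 0.5 the gain is equivalent to about 50/0.876² = 65 subjects analysed unadjusted.

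**FAS.** Entry requires FAS of at least 22, which may compress the baseline spread. If the baseline SD is 0.8 of the week-12 SD (assumed), Var(change) is proportional to 1 + 0.64 − 1.6ρ and the variance ratio is (1−ρ²)/(1.64−1.6ρ). After the covariate cost the width ratios are 0.896, 0.956, 1.002 and 0.992, so the gains are 10%, 4%, 0% and 1%.

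**Drop-out of 20% (20 per arm).** Unadjusted: 1.96 × 5.0 × √(2/20) = 3.10 and 1.96 × 6.7 × √(2/20) = 4.15. The covariate cost is √(37/36) × t(37)/t(38) = 1.0147.
- ρ = 0.5: ratio 0.879, giving ±2.72 to ±3.65
- ρ = 0.7: ratio 0.936, giving ±2.90 to ±3.88

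Adjustment therefore recovers about what drop-out costs at ρ = 0.5, but only part of it at ρ = 0.7.

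**Week-4 scores.** Suppose all 5 subjects per arm who lack week 12 have a week-4 score, with a common correlation between visits. The further gain is 1 − √(1 − (5/25)(ρ/(1+ρ))²) = 0.011 at ρ = 0.5 and 0.017 at ρ = 0.7. This is a best case of 1% to 2%.

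**The case against.** The plan is not wrong. Section 14.1 puts feasibility ahead of hypothesis testing, the outcomes are labelled secondary or exploratory, and no benchmark uses the arm difference. Aim 2b asks for the variability of changes, which the change-score summaries supply. The planned mixed model could carry the adjustment, so this may be brevity and not a decision against it. All of this stands, and it is why the point ranks as a free improvement only. It does not remove the gap, because estimating the treatment effect is also a stated objective and no text assigns that estimate to an adjusted model.

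The gain rests on an assumed correlation. The one related figure in the documents, 0.89, gives only 2%, and FAS, the symptom the app targets, may gain little. This also stands: 18% and 12% should not be read as expectations for FAS. Even so, the least favourable case examined for the baseline covariate alone is a width ratio of 1.002, which is practically neutral.

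The half-widths above keep the plan's 1.96 multiplier. With t quantiles the unadjusted range is ±2.84 to ±3.81, and the adjusted range is ±2.49 to ±3.34 at ρ = 0.5 and ±2.80 to ±3.75 at ρ = 0.89. Both sides widen by about 2.5% and the percentages are unchanged. At ρ = 0.89, however, a t-based adjusted interval is no narrower than the ±2.8 to ±3.7 printed in the plan.

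**Conclusion.** The concern holds as a low-cost improvement. Section 14.2 specifies only the unadjusted difference in change, although a more efficient estimate of the same effect is available from data the trial already collects. With equal variances at both visits and ρ between 0.3 and 0.89, the 95% interval narrows by 18% down to 2%. For FAS with a compressed baseline the range is 10% down to nothing. No conclusion on feasibility or usability changes. The size of the gain cannot be fixed more closely, because the documents give neither ρ nor the variance at each visit.

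**What to change.** Add to section 14.2 that the week-12 arm difference and its 95% CI are adjusted for the baseline score of the same outcome:

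- **FSE and TSRQ** (weeks 0 and 12 only): ANCOVA with arm and baseline score.
- **FAS, PSS and KSQ**: the mixed model already planned, with arm, visit, arm-by-visit and baseline score, reading off the week-12 contrast. Subjects with a week-4 but no week-12 score then contribute, in keeping with the intent-to-treat wording, though this adds little precision.

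Keep the change-score tables as descriptive output. Report the residual SD and the baseline to week-12 correlation, which a later baseline-adjusted trial will need for its sample size.

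Section 7 says randomisation is stratified by healthcare provider; the procedures in 9.1.3 do not repeat this. Include a provider term only if the sponsor confirms that the stratification was implemented and the strata are few. The reason would be agreement with the randomisation, not precision: if provider explains no variance, each extra stratum costs up to about 1% of interval width and could cancel the baseline gain at high ρ.

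The cost is a few sentences of SAP text and a few lines of code, with no new data or visits. The statistical price of the baseline covariate, about 1.1% of interval width at N = 50, is already deducted in the N = 50 figures above.

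### Section 14.2 does not say how the intent-to-treat arm difference of 14.1 is estimated when week-12 data are missing, and gives the mixed model that could supply it only a variance role

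*Combined protocol and SAP*

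**What the plan says.** Section 14.1 sets the sample "with 50 SPs (25 per group" and gives precision for the impact measures (PSS, FAS, QoL, FSE, TSRQ) in these terms: "in intent-to-treat analyses, 95% CI estimates of within-group change scores (pre- to post-treatment) will have precisions". The half-widths are ±1.5 to ±2.4 within group (the lower one is misprinted as 0.1.5) and ±2.8 to ±3.7 between groups.

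Section 14.2 then describes the analysis of the same measures: "Mean change and difference in change between the groups from pre-to-post intervention along with their 95% CIs will be reported". No analysis set, imputation or other missing-data method is attached. Patterns of missing data and attrition are to be examined, but no consequence for the analysis follows.

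The next step in 14.2 is a model: "Linear mixed-models for repeated measures will be used for the continuous impact measures to obtain estimates of intra-cluster correlation". The other stated outputs are variances and the covariance structure, for sizing a later trial. No treatment contrast is assigned to it.

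Three other places bear on this:

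- Section 7 makes estimating a treatment effect on stress, fatigue and quality of life part of the objective, and 14.3 anticipates signals of improvement over control.
- Sections 8 and 14.3 set retention at 80% or more, that is, drop-out of 20% or less.
- Table 2 schedules FAS, KSQ and PSS at weeks 0, 4, 12 and 24, and FSE and TSRQ at weeks 0 and 12 only.

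**The concern.** A baseline-to-week-12 change does not exist for someone with no week-12 value. With no missing-data method named and the mixed model given another job, the default calculation under 14.2 drops that person, including any week-4 FAS, KSQ and PSS already collected. That is not the intent-to-treat estimate whose precision 14.1 quotes.

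The arms also differ in a way that makes differential loss plausible. Only the SPARC arm has a 10-minute task twice a day for 12 weeks, and in the proof of concept trial adherence fell from 81% in month 1 to 65% in month 3 (one participant had started chemotherapy). If SPARC participants who feel no better at week 4 are the ones who leave, the remaining participants flatter the app. What is at stake is the exploratory effect estimate and the honesty of its confidence interval. The primary feasibility results are not affected.

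**Working it through.** **1. Reproduce the plan's precision.** Inputs from 14.1: 25 per arm; SD of change 3.7 to 6.1 within group; SD 5.0 to 6.7 for the between-group comparison; 95% confidence, z = 1.96.

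- Within group, 1.96 × SD / √n: 1.96 × 3.7 / √25 = 1.45 and 1.96 × 6.1 / √25 = 2.39. Stated: 1.5 and 2.4.
- Between groups, 1.96 × SD × √(2/n): 1.96 × 5.0 × √(2/25) = 2.77 and 1.96 × 6.7 × √(2/25) = 3.71. Stated: 2.8 and 3.7.

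The figures therefore assume a week-12 value for everyone randomised.

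**2. Precision if only participants with week-12 data are used, at the 20% limit (20 per arm).**

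| | 25 per arm | 20 per arm |
|---|---|---|
| Within group | ±1.45 to ±2.39 | ±1.62 to ±2.67 |
| Between groups | ±2.77 to ±3.71 | ±3.10 to ±4.15 |

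The widening is √(25/20) = 1.12, or 12%. If only one arm loses 20% (25 v 20), the between-group half-width is 1.96 × SD × √(1/25 + 1/20), giving ±2.94 to ±3.94.

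**3. Size of a possible bias.** Within an arm, the mean among those who stay minus the mean for everyone equals d × g. Here d is the drop-out proportion and g is the mean change of those who stay minus that of those who leave. The bias in the arm difference is d × g in SPARC minus d × g in control. With loss only in SPARC and d = 0.20, a gap of 2, 4 or 6 points gives 0.4, 0.8 or 1.2 points.

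A large-sample simulation replaces the assumed gap with an assumed mechanism: no true effect, change SD 5.0 to 6.7, week-4 to week-12 correlation of change 0.5 to 0.7, and log-odds of leaving after week 4 rising by 1 to 2 per SD of worse week-4 change.

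| Drop-out, SPARC v control | Bias towards SPARC, observed change | Bias, estimate using week 4 |
|---|---|---|
| 20% v 5.5% | 0.3 to 0.8 | about 0 |
| 20% v 0% | 0.4 to 1.2 | about 0 |
| 20% v 20%, same mechanism | about 0 | about 0 |
| Any of these, unrelated to outcome | about 0 | about 0 |

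The drop-out rates need not differ. With 20% in each arm but outcome-related loss in SPARC only (SD 5.5, correlation between visits 0.6, 25 per arm), the bias was still about 0.6 points.

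**4. What the mixed model changes at 25 per arm.** With 27% outcome-related loss in SPARC, 10% unrelated loss in control and no true effect:

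| Estimator | Mean estimate | Empirical SE |
|---|---|---|
| Observed change | -0.65 | 1.60 |
| Mixed model, free arm-by-visit means | 0.05 | 1.58 |
| Mixed model, common baseline mean | 0.01 | 1.45 |

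Both models remove the bias. The SE falls by 1 - 1.58/1.60 = 1% with free means and by 1 - 1.45/1.60 = 9% with the common baseline. The precision gain, 5 to 11% across the settings tried, therefore comes almost wholly from the baseline constraint and hardly at all from recovering the participants who left.

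**The case against.** The strongest reply is that 14.1 and 14.2 do not contradict each other: 14.2 is silent. Nowhere does it restrict the analysis to completers or observed cases, and it does not forbid taking the contrast from the mixed model. That stands. A reader might infer that the plan prescribes a completers-only analysis, but the documents support this only as the natural default for a simple change score.

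A reader might also infer that the effect estimate will be biased. The documents do not support that. Bias needs loss that is related to outcome and selection that differs between arms, and there is no evidence of either. The only attrition reported is 5.5% of 18. Stopping the app is also not the same as leaving the study: 14.2 lists the two separately, follow-up falls at routine clinic visits, and each evaluation is compensated. A 27% loss in SPARC is an assumption above the anticipated 20%.

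Nor do the documents exclude week-4 and week-24 comparisons. Section 9.1.3 defines the secondary outcomes as group differences in change without fixing a visit; 14.2 simply specifies only the pre-to-post one.

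Finally, the trial's focus is feasibility "rather than hypothesis-testing". What 14.2 says will inform the next trial is the variance and covariance information, which already comes from the mixed model. That limits the consequence. It does not remove the gap, because an estimator left open can be chosen after the data are seen.

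**Conclusion.** The point holds as a gap between the intent-to-treat promise in 14.1 and the estimator described in 14.2. It is worth fixing, but it does not threaten the primary conclusions.

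Two results need no assumed drop-out mechanism: the stated half-widths require all 25 per arm, and at the plan's own 20% limit an analysis of observed changes would be about 12% less precise. The bias of about 0.3 to 1.2 points is conditional on the assumed mechanisms and is smaller than the planned half-width of 2.8 to 3.7 points.

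The near-zero bias of the model also depends on an assumption, namely that loss depends only on values already observed. It would not protect against loss driven by the unseen week-12 value. For FSE and TSRQ, which have no visit between baseline and week 12, the model can draw only on baseline and the gain is small.

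**What to change.** In 14.2, state that the week-12 arm difference and its 95% CI for each impact measure come from the mixed model already planned, and likewise the week-4 and week-24 differences for FAS, KSQ and PSS. Specify:

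- all randomised participants with any observation, analysed as randomised;
- visit and arm-by-visit terms with a common baseline mean across arms;
- unstructured covariance over visits;
- the missing-at-random assumption, with a note that for FSE and TSRQ this means missing at random given baseline.

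Keep the raw mean changes as descriptive, with the number contributing in each arm. In 14.1, correct the misprint 0.1.5 to 1.5 and add the half-widths at 20% loss. If a precision gain is mentioned, attribute it to the common baseline.

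The cost is a few sentences. No extra participants, visits or data are needed, and the model is to be fitted anyway.
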